Individuals who are able/willing to participate

Individuals who are able and willing to participate will be asked to return their consent form and questionnaire to us. They will then be contacted within one month to schedule examination 1. If someone wishes to participate but is unable to complete examination 1, we will ask for their consent to use data from the questionnaire and link it to various registries.

Examinations

Questionnaire

Questionnaires will be labeled with barcodes to link them to individuals. The key that links barcode to personal identification number will only be stored in the database. The procedures for assigning project numbers, printing barcodes, and linking to personal identification number will be the same as previously used in HUNT3 (approved by REK and the Norwegian Data Inspectorate). In addition to being uploaded to the database by optical scanning, questionnaires will be stored at the research unit. Participants will receive a new questionnaire one year, three years, and five years after examination 1. The majority of questionnaire questions were used in HUNT3 (approved by HUNT Research Center).

Clinical examinations

Participants will be asked to attend medical examinations at baseline after one year, three years and five years. The following clinical tests will be performed:

- Medical screening with interview and checks of Consent signed
- Assessment of general health status

- Weight, height and waistline measurements
- Maximal oxygen uptake, maximal heart rate, heart rate 1 minute after testing

All data will be recorded both manually and electronically. A Case Report Form (CRF) will be completed for each participant, and forms will have a code linking the data to the participant. Forms will be entered into the project database by optical scanning. After scanning, forms will be locked and stored securely at the K.G. Jebsen Center for Exercise in Medicine, where only data supervisors will have access.

Links to registries

Participants consent to give the medical supervisor of Generation 100 access to medical records. In addition, we plan to connect our data to the Cause of Death Registry and Statistics Norway. Patient archive system of the community hospitals will be used to identify clinical outcomes (CVD and Cancer).

Follow-up

The participant may be contacted 10 years after inclusion of the study with a request to repeat basic examinations. Participation in follow-up examinations is voluntary.

Randomization

Participants are randomized (stratified by sex and cohabiting status) into one of two groups: an exercise training group or a control group. The exercise training group will again be randomized to either high-intensity training or moderate-intensity training. Spouses/partners will be randomized into the same group. The randomization will be performed after the completion of all basic examinations at examination 1. The Unit for Applied Clinical Research at NTNU is developing a web-based randomization procedure to ensure impartial assignments. After randomization, participants will receive verbal and written information about how to exercise and record their training.

Sample size and statistical power

The primary endpoint of the study is overall mortality. According to Statistics Norway, approx. 2% in this age group die every year. Currently, there is no data that indicates the magnitude of the effect of exercise on the reduction in mortality, but from observational studies a 50% reduction has been reported. With a 50% reduction in mortality rate, and a power of 90% (p<0.05), 1200 participants are needed (600 in each group). We will try to include 1500 participants to allow for drop-out (approximately 20%).

Intervention

Choice of intervention

Clinical studies have shown that high-intensity exercise training gives a greater increase in VO_{2max} and better cardiovascular adaptations than low- or moderate-intensity training (20, 22, 23). However, little research has been done on an elderly population, and it is unknown which intensity gives the greatest effect on morbidity, mortality and functional capacity in this group. Therefore, we believe that it is important to compare individuals who exercise at moderate and high intensities. Additionally, we think it is important to have a control group that receives current recommendations for physical activity.

High-intensity training group

This group will be asked to complete high-intensity exercise training two times per week. Different models will be described, but interval training will be the primary focus. Participants in this group will be asked to complete approx. 30-minute-long workouts. During this half hour, participants should reach at least 16 on the Borg scale for perceived exertion four times. In the course of 30 minutes, they should be very short of breath four times, each for a duration of approx. 4 minutes. We have previously used the 4x4 model with success and will present it to participants. Sessions start with a light 10-minute warm-up, followed by four 4-minute working periods interspersed by 3-minute active breaks. The intensity during the working periods should be 85-95% of maximal heart rate, corresponding to approx. 16 on the Borg scale. Breaks will consist of relaxed walking, down to 12 on the Borg scale. Within one month of the first examination, participants will attend a group meeting where the principles of training and reporting physical activity will be reviewed thoroughly (see paragraph on reporting exercise training). At the information meeting, participants will also receive information about the various group training sessions available to them. Group sessions with both indoor and outdoor activities will be arranged at various locations near Trondheim City Center three times per week. Participants may choose between a variety of activities (these will vary from week to week), such as: walking/running, spinning, dance, and aerobics. An exercise supervisor will be present at all sessions arranged by the study. Attendance is voluntary, and participants may choose to perform their exercise training individually if they prefer.

Moderate-intensity training group

This group will be asked to complete 50 minutes of continuous moderate-intensity exercise corresponding to 70% of maximal heart rate – approximately an isocaloric workout compared to the sessions performed by the high-intensity training group. For most, this will be perceived as "talking pace." The workout should be perceived as approx. 13 on the Borg scale. Within one month of the first examination, participants will attend a group meeting where the principles of training and reporting physical activity will be reviewed thoroughly. At the information meeting, participants will also receive information about the various training sessions available to them. Group sessions with both indoor and outdoor activities will be arranged at various locations near Trondheim City Center three times per week. Participants may choose between a variety of activities (these will vary from week to week), such as: walking/running, spinning, dance, and aerobics. An exercise supervisor will be present at all sessions arranged by the study. Attendance is voluntary, and participants may choose to perform their exercise training individually if they prefer.

Spinning sessions

Every sixth week the two training groups met separately for obligatory supervised spinning sessions (ergometer cycling) with an exercise physiologist, where they exercised with heart rate monitors to ensure recommended exercise intensities.

Control group

The group will be asked to follow current recommendations for physical activity (Norwegian Directorate of Health, 2011), but will not receive further supervision.

Reporting exercise training

Participants in the training group will receive a training log. In addition to general information about the exercise, the log will consist of scannable forms to be completed after each exercise session. Each month, participants will send their exercise logs to the research center either by prepaid envelopes, internet-based forms, or email. Reporting will be done by use of a system with well-established web-based forms and prior approval (Visma or Questback). For closer monitoring of exercise training and activity levels, some participants may at times be

supervised by activity monitors, lactate measurements and heart rate monitors. This will be done to see if self-reported training corresponds to actual physical activity and intensity.

Follow-up and reminders about training logs

Participants who do not submit their training logs will be contacted within 14 days – once by telephone/Internet and once by mail to request the logs.

Safety

If anyone experiences discomfort during training, they should report this to one of the research supervisors, who will immediately contact the medical supervisor. The research supervisor and medical supervisor will together determine if the event should be reported to the safety committee (more information below) and if the participant should be referred to further medical care.

Stopping criteria for training

Any participant who falls under an exclusion criterion during the study should cease exercise training. For CVD patients the following conditions will count as stopping criteria for exercise training: progressive signs of heart failure (increasing breathlessness during low-intensity exertion, nighttime breathlessness, or edemas), new angina or rapid worsening of angina at low intensities, signs of sudden-onset angina at rest.

Information to participants

Individual

All participants will receive an informational brochure in the mail. This will consist of two parts: A) a brief, tangible, and simple information sheet describing the examinations that will be performed and what the data will be used for, and B) a more detailed description of examinations, what participation entails and how data will be treated. The informational brochure will contain contact information so participants can get their questions answered. The data that is collected in the study may in the future be used for a variety of research projects that cannot currently be predicted; hence it is impossible to inform participants about all projects that will use data from the study. We will emphasize transparency about our primary objectives.

Verbal and written information

All participants will receive verbal and written information about the study, and training guidelines for their assigned intervention. Participants will also receive directions for how to fill in training logs and report back to the researchers. Where possible, participants may elect to receive copies of their test results (e.g. measured fitness, waistline, lipid levels, blood pressure and resting heart rate). Participants will be notified if examinations and/or test results indicate the need for further medical care. The medical supervisor will evaluate if the need for follow-up is immediate – resulting in additional care within a few days – or if referral to primary care is adequate.

Informational meeting

Within one month of examination 1, all participants will be invited to attend informational meetings. These will be held according to group allocation, so participants randomized to the same intervention will attend the same informational meeting.

Internet

There will be extensive updated information about the project on the research group's website: www.ntnu.no/cerg/generasjon100.

Data management

Voluntary participation and consent

All participants recruited to join the study do so voluntary. All who would like to, and who meet the inclusion criteria, will be invited to attend examination 1. At examination 1 (prior to testing) all participants must give written consent that they wish to join the study. It is very important to us that the information about the study provided to participants is sufficiently clear that they can give an informed consent where they understand what participation entails. Participants may at any time withdraw their consent without providing an explanation. Individuals who are excluded during the course of examination 1 or change their mind about participating afterwards may themselves decide if the data already collected about them may be used in the study. We will inquire about why participants no longer wish to be a part of the study, but it is up to the individuals to decide if they want to give a reason or not. All data will be treated confidentially in order to maintain privacy during data processing. All project employees are bound by confidentiality and must sign a non-disclosure agreement. The project will be completed according to the principles of the Declaration of Helsinki. It must be approved by the Regional Committee for Medical and Health Research Ethics prior to start.

Databank

We will create a project databank at the HUNT Research Center. Data from the databank will be available to a variety of research fields for many years to come. Although it is currently challenging to predict all future uses of the material, the purpose of the project is to determine if exercise training has an effect on major health issues for the elderly population in Norway. Any other projects must apply for permission to access and use the data, and a collaboration agreement must be signed by both parties.

Biobank

We will create a separate project biobank. It will be located at St. Olav's Hospital, Emergency, Heart and Lung Center. [name] will be responsible for the biobank. Participants who sign the consent also agree to the inclusion of biological materials and analysis results in the project biobank. Data in the biobank will be anonymized, and only select authorized personnel (4 people) will have access to the identification key linking serial number to participant identity. We wish to store the data for 10 years after completion of the study, i.e. until 2025. Afterwards we will seek REK approval to move remaining samples to the HUNT biobank in Levanger, Norway.

Privacy

All data from the study is theoretically identifiable, i.e. tied to an 11-digit personal identification number. Personal identification number will only be used if necessary, and only a few individuals (4 data supervisors) will have access to the original file. There will be an IT safety binder (from HUNT3) that all data supervisors will read and be familiar with. The data will be anonymized during analysis and when files are provided to others. This means that all personal identifiers such as name, birthday, address, etc. will be removed and replaced by a project-specific code. New integrated IT-systems were developed for use in the third Nord-Trøndelag Health Study (HUNT3), with an emphasis on addressing privacy concerns. The Generation 100 will use the data systems developed for HUNT3 to collect, manage, and store

data. The procedures have been developed in close collaboration with the Norwegian Data Inspectorate and REK and are approved by both.

Data security

The data collected at the examinations will be entered into the database both manually and electronically. Anonymized data files will be treated with the same level of security as identifiable data files with respect to storage and access.

Insurance

All participants are insured by Norwegian Patient Injury Compensation (Norsk Pasientskadeerstatning).

Ethical aspects

Information

Generation 100 is an extensive study, and it is challenging to provide sufficient information to individual participants. Providing sufficient clear information is a high priority, so that participants feel that they know what consenting entails. Moreover, participants will have the opportunity to ask questions at all examinations and informational meetings.

Advantages

There is strong evidence suggesting that regular exercise training gives better health than inactivity. Additionally, participants will learn about exercise, physical activity and health. Participants will receive a wide variety of clinical examinations and follow-up care that they would not have had otherwise (including the control group).

Disadvantages

The risk of exercise is considered very small; however, the risk of complications/death is higher during and immediately following training/testing. Nevertheless, the health benefits from exercise training are sufficiently high that it is considered less harmful than inactivity. All methods have been tested thoroughly by both healthy individuals and various risk groups and are not considered risky or thought to have negative side effects. There will be at least two doctors working in the project, who are available if unforeseen problems should arise.

Information security

A lot of sensitive data will be collected and must be handled properly. It is an advantage that the information systems we will use have been developed by HUNT in collaboration with the Norwegian Data Inspectorate and already have been approved by REK. Whenever possible we will use barcodes instead of personal identification numbers during data collection. Only 4 data supervisors will have access to data files with identifiable information.

Different training groups

The control group will not have access to supervised exercise training. However, they will be advised to follow current guidelines for physical activity. This group will receive "worse" follow-up care than the two other groups. Nevertheless, this reflects the current state of affairs, and we deem it necessary to have a control group receiving the "treatment" currently offered to the public.

Steering committee

The steering committee is the study's executive body. They have developed the study protocol and are responsible for data collection, management and publication. All major

scientific and ethical questions will be resolved by majority vote. The group is responsible for finding solutions to unforeseen questions/problems that arise in the course of the study. The steering committee consists of the following people: [name], PhD [name], MD [name], PhD [name], [name], [name], PhD and [name] [name], PhD.

Safety committee

All serious events that occur during the study should be reported to the research unit, which in return will report the event to a safety committee within one week. A research supervisor will fill out a safety report describing the event. Serious events are defined as: medical treatment resulting from the onset of new cardiovascular disease/events, or injuries/fractures. The committee will determine if the groups differ, and if it is ethically justifiable to let the study continue. Participants are encouraged to contact researchers if something unforeseen should occur; additionally, the safety committee will access the various registries once per year to obtain relevant data. The safety manager will be [name], Professor at the Department of Circulation and Medical (ISB), NTNU.

Funding

The project will primarily be funded by the K.G. Jebsen Center for Exercise in Medicine. Other major contributors include: Central Norway Regional Health Authority, the Norwegian Research Council, the Norwegian Association for Public Health, and NTNU.

Scientific significance and dissemination

The study will be unique in several ways. It will give the largest cross-sectional data on the elderly in Norway, especially with respect to fitness level, cardiovascular health and functional capacity. It will also be the largest and longest randomized study investigating the effects of exercise on morbidity and mortality. The data collected will be sufficient for a multitude of future research studies. This type of study generally garners widespread interest and media attention and should be of a sufficiently high standard to be published in renowned international scientific journals. We anticipate that the project will determine if exercise – potentially of different intensities – has an impact on morbidity and mortality. In light of the aging population, our data will hopefully contribute to an improved understanding and examples of possible eldercare solutions. Research to improve prevention and treatment will benefit a large proportion of the population and may give a significant economic benefit to society. The goal of the study is to determine if exercise training has an impact on several major health issues that affect the elderly population in Norway.

Summary of changes Protocol

The following amendments to the original protocol have been made.

- Amendment No1; Inclusion and exclusion criteria August 2012,
- Amendment No2, Safety Committee, June 2013
- Amendment No3: Outcome measures July 2013
- Amendment No4; Drop-outs, August 2013
- Amendment No5; Primary and Secondary outcomes, October 2014

Amendment No1.

Due to safety reasons during the clinical testing, we excluded people with chronic communicable infectious diseases. In addition, we realized that the inclusion criterion "must be able to walk at least 1 km", was hard to test, and this criterion was changed to "able to complete the exercise program (determined by the researchers). Also, the criterion "active cancer" was changed to "cancer that makes participation impossible or exercise contraindicated. Considered individually, in consultation with physician". These changes were included in the protocol 08. August 2012, before the inclusion of the first patient. We realized that the number of participants included was lower than expected. We therefore expanded the age-range and included also people born in 1936 and 1937.

Amendment No2.

[name] were not able to be a part of the safety committee, thus [name] become the safety manager in the study. Changes made in June 2013.

Amendment No3.

By a mistake the outcome was change in July 2013. The reported outcome measures were related to the first PhD project, and instead of registering a new clinical trial, the candidate added the primary aims to the original trial. The mistake was noticed in May 2014, and the primary outcome was then changed back to what has always been the main outcome, mortality.

Amendment No4.

In August 2013 reasons for drop-out was changed to comprise; excluded, withdrew or died. Thus, participants who stops training for more than 6 months due to any reason, but still wanted to be in the study, were not excluded.

Amendment No5.

In October 2014, the principal investigators changed the primary aim to be more specific and clearer, and changed the secondary outcomes of the study to include changes in cardiovascular diseases, cancer, and peak oxygen uptake. Change in risk score, physical activity level, hospitalization, physical function capacity, medication, use of health care services, and development of dementia and depression will be presented in separate studies.

Original Statistical analysis plan

As specified in the protocol paper the primary combined endpoint of the study is overall mortality (24). Further, as described in the protocol paper (24); "All comparisons of change between the groups will be done by the intention-to-treat principle. Thus, data will be analyzed according to the group participants were assigned to, regardless of possible crossover and/or adherence to the intervention. Non-adherence will be defined as having performed less than 50% of the prescribed training sessions over the five years. Survival and morbidity analysis will be done by performing chi-square and log-rank tests. Cox regression analyses will be used to compute hazard ratios of all-cause mortality and onset of new diseases between the groups. The precision of the estimates will be assessed by 95% confidence intervals. All statistical tests will be two-sided."

Final Statistical analysis plan

The original plan was not very specific on how the analysis would be performed; thus, a more detailed plan was formed before (13 February 2019) any analysis was conducted. For the VO_{2peak} and SF 8 we plan to use a linear mixed model with the clinical variables one at a time as dependent variable. Time point (0,1,3,5 years), intervention group, and their interaction as categorical covariates, and participant nested within cohabiting pair as random effects. Participants had been randomized such that a cohabiting pair was randomized to the same group. Hence, it is appropriate to use a three-level mixed model, with participant nested within cohabiting pair. In addition, we adjust for variables used as stratification variables in the randomization (sex, cohabitation status). We will adjust for age at inclusion, which is plausibly important prognostic factor, as recommended by (25) and (26). In the mixed model, we will adjust for baseline as recommended by (27). Normality of residuals will be checked by visual inspection of QQ plots. In these analyses, if a person is dead, we regard that as missing data after the person is dead. In a sensitivity analysis, we will exclude the persons who died during the study from the analysis. The main analysis for survival, will be a Cox proportional hazards regression, adjusting for the covariates listed above.

Summary of changes Statistical analysis plan

The following amendments to the original statistical analysis plan have been made.

• Amendment No1; Exclusion of VO_{2peak} data

Amendment No1:

Participants should have been tested on the same machine (treadmill or bike) at every examination. For those who had test both on treadmill and bike, we deleted the bike measurements. In total 41 persons had data both from treadmill and bike, bike measurements were deleted, and values given as missing.

References

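### The serious-event definition does not name death, so some deaths may reach safety review only at the yearly registry check, and injuries/fractures have no named source that covers all arms

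*Supplement*

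**What the plan says.** All places are in the final protocol unless stated.

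- **Safety committee, definition:** "Serious events are defined as: medical treatment resulting from the onset of new cardiovascular disease/events, or injuries/fractures".
- **Safety committee, timing:** such events go to the research unit, "which in return will report the event to a safety committee within one week".
- **Safety committee, judgement:** "The committee will determine if the groups differ, and if it is ethically justifiable to let the study continue". Neither the final protocol nor the final SAP says how a difference is to be judged.
- **Safety committee, second source:** "the safety committee will access the various registries once per year to obtain relevant data". The registries are not named there.
- **Links to registries:** "we plan to connect our data to the Cause of Death Registry and Statistics Norway". The community hospitals' patient archive is to supply cardiovascular and cancer outcomes. Injuries and fractures are not mentioned.
- **Disadvantages:** "the risk of complications/death is higher during and immediately following training/testing".
- **Reporting exercise training** (training groups only): "Each month, participants will send their exercise logs to the research center". Participants who send no log are contacted again. The training groups also have obligatory supervised cycling every sixth week.
- **Control group:** advised to follow national guidance, with no further supervision. The Different training groups section concedes that this group's follow-up is poorer.

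**The concern.** Two things are at stake.

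The first is the speed of case review. The protocol identifies death around training or testing as a known risk, yet the rule that triggers a one-week report is written around treatment for new cardiovascular disease, and injuries. Participants may train on their own. Someone who dies at home after a session without being treated does not meet the cardiovascular wording. A death from any other cause apart from injury is outside it even when treated.

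The second is the comparison between groups. The same section asks whether the groups differ and whether the study may go on. If spontaneous reports feed that judgement, an arm in regular contact with the research unit has more occasions to report than one seen at years 1, 3 and 5. An apparent excess of harm under exercise could then arise from reporting alone. The exposure is greatest for injuries/fractures: they are in the definition, but no source covering all arms is named for them.

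**Working it through.** **1. The plan's own figure.** Sample size and statistical power gives 2% mortality per year, a 50% reduction, 90% power, p<0.05 and 600 per group. Take five years as 5 × 2% = 10% in controls and 5% under exercise, two-sided (stated in the original SAP):

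n per arm = [1.960 × √(2 × 0.075 × 0.925) + 1.282 × √(0.10 × 0.90 + 0.05 × 0.95)]² / 0.05² = 582 after rounding up, or 1164 in total. This is within 3% of 1200, and 1200 / 0.80 = 1500. The plan's rates are therefore understood correctly, and nothing here disputes the sample size.

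**2. Deaths the definition does not name.**

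| | N = 1200 | N = 1500, before drop-out |
|---|---|---|
| Control deaths | 600 × 0.10 = 60 | 750 × 0.10 = 75 |
| Exercise deaths | 600 × 0.05 = 30 | 750 × 0.05 = 37.5 |
| Total | 90 | 112.5 |
| Non-cardiovascular, at 1 − 0.36 = 0.64 | 57.6 | 72 |

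The 36% is the national cardiovascular share quoted in the Physical activity section; applying it to this cohort is an assumption. The non-cardiovascular deaths, apart from injury deaths (share not given), are outside the definition even if treated. The remaining 90 − 57.6 = 32.4 cardiovascular deaths are inside it only if treatment was given. Most of these deaths will have nothing to do with training. How many would follow a session closely cannot be derived from the documents.

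**3. Delay.** A reportable event reaches the committee within one week of the research unit's report. A death outside the definition may wait for the yearly check: up to about 12 months, plus any registry lag, which is not stated.

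**4. Contact by arm over five years.**

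- Exercise: 5 × 12 = 60 monthly logs, and about 5 × 52 / 6 ≈ 43 supervised cycling sessions.
- All arms: an information meeting and examinations at years 1, 3 and 5.

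These are occasions for contact, not counts of adverse-event reports. The logs are exercise forms and are not said to collect adverse events.

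**5. What unequal capture would do.** The documents give no capture rates, so these are assumed. With equal true rates, apparent ratio = capture in exercise / capture in control:

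- 0.90 / 0.90 = 1.00
- 0.90 / 0.70 = 1.29
- 0.90 / 0.50 = 1.80

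Where all arms are read from one source with the same completeness, the ratio is 1.00.

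**6. Which events have such a source.**

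| Event | Source covering all arms in the final protocol |
|---|---|
| Death | Cause of Death Registry |
| Cardiovascular disease | Hospital patient archive |
| Injuries/fractures | None named |

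**The case against.** The strongest reply is that the safeguards are wider than the definition. All-cause mortality is the primary endpoint, the Cause of Death Registry is linked, and the committee consults registries every year. A reader might infer from the definition that fatal events can be missed altogether. The documents do not support that: the deaths are delayed. A collapse at a supervised session or test may also lead to treatment and so be reportable, and discomfort in training has its own route through the medical supervisor. What remains is the death that is untreated, or neither cardiovascular nor due to injury, for which no prompt report is required.

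A reader might also infer that the group comparison rests on spontaneous reports and is biased. That goes too far. Nothing confines the judgement to such reports, registry access does not differ by arm, and the hospital archive covers cardiovascular disease in all arms. Participants in every arm are encouraged to contact the researchers. Bias is possible, not shown, and chiefly concerns injuries/fractures.

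Finally, a reader might infer that yearly looks without a boundary inflate the type I error of the mortality test. Five two-sided looks, each at 5%, would give about 14%, but the documents contain no such procedure. They state no interim test, no interim significance level and no stopping for benefit, so no error rate can be attached to the committee's judgement.

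**Conclusion.** The concern holds in a limited form and should be corrected. Death is absent from the serious-event definition although the protocol names it as a risk of training and testing. On the plan's rates about 90 deaths are expected at 1200 participants. About 58 of them, less any injury deaths, would be outside the definition whatever treatment was given, if the national cardiovascular share applies. The consequence is delay of up to about a year plus registry lag.

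Unequal capture is a risk for spontaneously reported non-fatal events, most of all injuries/fractures. Its size is unknown: the range of 1.0 to 1.8 rests wholly on assumed capture of 90% against 50-90%, and it vanishes where all arms are read from the same source.

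**What to change.** 1. Add death from any cause to the serious-event definition, in all arms and whether or not treatment was given, so that the one-week report applies to it.
2. Base the between-group comparison on events drawn identically in all arms each year from the Cause of Death Registry and the hospital patient archive. Extend the archive search from cardiovascular disease and cancer to injuries/fractures; without that step the events most open to unequal reporting would drop out of the comparison. Keep spontaneous reports for review of individual cases only.
3. In the Safety committee section, replace the unspecified reference to registries with the sources that the final protocol actually links.

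The cost is protocol wording and a slightly wider yearly archive search. The death registry and the archive are already planned sources; the injury/fracture search is the only addition. No figure in the sample size or the SAP changes.
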